#### Accrual goals

The accrual goals for the patients at initial presentation are 40 for gastric and 35 for non-gastric MALT lymphoma. Based on the expectation that the relapse rate after radiation therapy alone will be 25% and that 70% of the relapsing patients will fail within 5 years, these numbers will provide a 95% confidence bound of +/- 5.9% for estimating the 2-year RFS. This calculation assumes that RFS follows an exponential distribution and we will follow all patients for at least 2 years.

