#### Stopping Rules for patient accrual at initial presentation

Based on the expectation that the relapse rate after radiation therapy alone will be 25% or less, RFS will be evaluated in each of the two subgroups of previously untreated patients and accrual stopped in RFS is < 70% after the first 15, 30, or 45 patients have been followed for a minimum of 2-years. Assuming that 70% of the relapsing patients will fail within 5 years, computer simulations indicate that this stopping rule will terminate patient accrual in both the gastric and non-gastric arms of the trial with a probability of 1% if the relapse rate is 25% with a 17% probability if the relapse rate is 50%, and with a probability of 60% if the relapse rate is 75%.

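### The stopping probabilities of 1%, 17% and 60% are worded as the chance of closing both arms, but they reproduce only as single-arm figures

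*Combined protocol and SAP*

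**What the plan says.** All of this is in section 11.0 of the combined protocol and SAP.

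- Under the stopping rules for accrual at initial presentation, "RFS will be evaluated in each of the two subgroups of previously untreated patients", and accrual stops if "RFS is < 70% after the first 15, 30, or 45 patients have been followed for a minimum of 2-years".
- The operating characteristics come from computer simulations: "this stopping rule will terminate patient accrual in both the gastric and non-gastric arms of the trial with a probability of 1"%, which is the figure for a 25% relapse rate. For relapse rates of 50% and 75% the plan gives 17% and 60%.
- The timing assumption is "Assuming that 70% of the relapsing patients will fail within 5 years".
- The accrual goals are 40 gastric and 35 non-gastric patients at initial presentation. For the precision of the 2-year RFS, the plan adds: "This calculation assumes that RFS follows an exponential distribution and we will follow all patients for at least 2 years".
- The opening paragraph says that accrual and outcome are analysed separately by group.

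The section does not say whether the simulations were run for one arm or jointly for two.

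**The concern.** The rule works arm by arm, on different patients, but the probabilities are attached to an event in both arms. If each arm can stop on its own data, the chance that both stop is lower than the chance that a given one stops. One set of three numbers cannot serve for both events.

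This sentence is the only statement of how the RFS stopping rule performs, and the section says that there is no stopping rule based on toxicity. Someone judging the rule's protection has to rely on it. Taken at its word, it says that both arms would close with 60% probability if three-quarters of patients eventually relapse.

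**Working it through.** **Inputs**

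- Relapse rates R of 25%, 50% and 75%, with 70% of relapses by 5 years (stopping-rule paragraph).
- Exponential time to relapse among those who relapse. The plan states an exponential model for the precision calculation; using one here is an assumption.
- Looks at 15, 30 and 45 patients, stopping if RFS is below 70%. I took RFS as the simple proportion relapse-free at 2 years. The boundaries are then more than 4.5, 9 and 13.5 relapses, that is at least 5, 10 and 14.
- Goals of 40 and 35 (accrual-goals paragraph).

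**Step 1: relapse by 2 years**

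From 1 − exp(−5λ) = 0.70, λ = −ln(0.3)/5 = 0.2408 per year. The share of relapses that occur by 2 years is 1 − 0.3^(2/5) = 0.382. The 2-year relapse probability is 0.382 × R:

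- R = 25%: 9.6%
- R = 50%: 19.1%
- R = 75%: 28.7%

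**Step 2: reproduce the plan's figures with one arm**

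An exact sequential binomial calculation gives the probability of first crossing the boundary at each look.

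| R | At 15 | At 30 | At 45 | Total | Plan |
|---|---|---|---|---|---|
| 25% | 1.05% | 0.01% | 0.00% | 1.07% | 1% |
| 50% | 14.2% | 1.3% | 1.0% | 16.5% | 17% |
| 75% | 43.8% | 7.8% | 7.5% | 59.2% | 60% |

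All three totals are within one percentage point of the plan.

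**Step 3: could the figures be joint?**

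With two independent arms and the same relapse rate, joint probabilities of 1%, 17% and 60% need single-arm values of √0.01 = 10%, √0.17 = 41% and √0.60 = 77%. I varied the boundary (at most 70% instead of below 70%), the set of looks, the shape of the relapse-time distribution and the way RFS is estimated at each look. No variant gave the three stated figures as joint probabilities.

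**Step 4: both arms, looks as written**

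For a single-arm probability p, both arms stop with probability p² if the arms are independent and share the same relapse rate:

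- R = 25%: 0.0107² = 0.01%
- R = 50%: 0.165² = 2.7%
- R = 75%: 0.592² = 35%

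Squaring the plan's rounded figures gives nearly the same: 0.01%, 2.9% and 36%.

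**Step 5: looks that the accrual goals allow**

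Both goals are below 45, so only the looks at 15 and 30 remain. The per-arm figure is the sum of the first two columns in step 2. The chance that at least one arm stops is 1 − (1 − p)².

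| R | One arm | Both arms | At least one arm |
|---|---|---|---|
| 25% | 1.1% | 0.01% | 2.1% |
| 50% | 15.5% | 2.4% | 28.6% |
| 75% | 51.7% | 26.7% | 76.7% |

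**The case against.** The strongest reply is that nothing was miscalculated. The preceding sentence applies the rule to each subgroup, the section analyses the groups separately, and the figures match a single arm closely. A sympathetic reader would take the sentence to mean that the same probabilities hold in each of the two arms. That reading is plausible, and it is why this is a fault of labelling. A reader might infer from the mismatch that the simulation is wrong. The documents do not support that, since step 2 reproduces it.

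A second reply is that no decision uses the joint probability. Each initial-presentation arm closes on its own data, and the previously treated groups have a separate decision, so closing both arms is not defined as stopping the trial. This also stands. A reader might infer that the plan overstates a whole-trial safeguard, but the plan contains no whole-trial RFS rule. Per-arm figures are what a per-arm rule needs, and joint figures are only an optional addition.

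A third reply is that 35% is not the trial's figure either, because it counts a look at 45 patients that neither arm reaches. That is correct. It lowers the both-arm figure at a 75% relapse rate to 26.7%, so it widens the gap from the printed 60%.

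What remains is that the sentence is wrong as literally worded, and that a reader cannot tell which event was simulated without rebuilding the calculation.

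**Conclusion.** The point holds as a mislabelled operating characteristic. The 1%, 17% and 60% are per-arm probabilities for looks at 15, 30 and 45. As probabilities of closing both arms they are too high: about 6-fold at a 50% relapse rate (17% against 2.7%) and 1.7-fold at 75% (60% against 35%), for the looks as written. For the looks that the goals allow, even the per-arm figure at 75% falls from about 59% to about 52%. The figures at 25% and 50% change little.

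The per-arm match rests on exponential time to relapse among relapsers and a simple 2-year proportion. The both-arm and at-least-one-arm figures also need independent arms with the same true relapse rate, which the documents do not state.

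All these figures are chances of crossing the boundary at a look. They do not allow for an arm having finished accrual before the look takes place. At the lowest expected accrual, if enrolment continues during follow-up, the 30-patient look falls when about 30 + 2 × 10 = 50 gastric or 30 + 2 × 5 = 40 non-gastric patients would have entered, against goals of 40 and 35. The chance of actually halting accrual is therefore lower than the figures above.

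**What to change.** In the stopping-rule paragraph, replace the reference to both arms with *in each arm separately*. Restate the per-arm probabilities for the looks that the accrual goals allow. With looks at 15 and 30 these are 1.1%, 15.5% and 51.7% under the assumptions above; if the looks or goals are changed, recompute them. State the relapse-time model used and that each arm was simulated on its own.

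The both-arm probabilities (0.01%, 2.4%, 26.7%) and the at-least-one-arm probabilities (2.1%, 28.6%, 76.7%) may be added, with the assumptions of independence and equal relapse rates stated.

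The cost is one sentence and a short recalculation, with no change to the design. The downside is that the stated stopping probability at a 75% relapse rate becomes less favourable, falling from 60% to about 52% per arm.

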#### Stopping Rules for patient accrual upon failure to other treatments

When the accrual goals of both gastric and non-gastric MALT lymphoma patients at initial presentation are met, the data for the patients who presented upon failure to other treatments will be analyzed. Decision regarding continued accrual of the patients will be made on the RFS outcome and patient accrual rate at that time.

As toxicity of 3 or higher is not expected, we do not have a stopping rule based on toxicity. However, any toxicity of 4 or 5 will be immediately investigated (see 12.1)

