
The data on the outcomes of the patients who relapse after initial treatment are lacking. The same statistical analysis and stopping rule will apply to the patients who are enrolled in this protocol after failure to initial treatment, though this may be very stringent criteria for this patient population.

2.2 Preliminary Data- We have recently reported our experience with 39 consecutive patients with MALT lymphoma with supradiaphragmatic presentation seen at M.D. Anderson Cancer Center between 1991 and 1997 (34). Ten of them were treated with radiation therapy alone. Two of them had stage 2 disease. The median dose was 39.6 Gy at 1.5 to 2.0 Gy per fraction. Everyone achieved a clinical complete response. At a median follow-up of 26 months, everyone is alive. Two patients experienced recurrence. Both of the recurrences were in the stomach. They were successfully salvaged, rendering every patient free of disease at the last follow-up. Of note is six of these 10 patients had primary conjunctiva lymphoma making the scope of this experience quite limited. We now propose to extend radiation treatment as the only modality to stage 1 and 2 non-gastric MALT lymphomas in general.

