## 11.0 Statistical Considerations and Stopping Rules

This is a trial to estimate the relapse-free survival rate (RFS) of patients with gastric and non-gastric MALT lymphoma treated with radiation therapy alone. Patient accrual is expected to be 10 – 15 per year for gastric and 5 – 10 per year for non-gastric MALT lymphoma at initial presentation. Accrual of less than 5 patients per year for either gastric or non-gastric MALT lymphoma is expected for presentation upon failure of other treatment modalities. The patient accrual and outcome analyses will be done separately in the following 4 groups: Gastric vs non-gastric MALT at initial presentation vs upon failure to other treatment(s).

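### Section 11's only RFS review of prior-failure patients waits for both untreated arms to reach their goals, so as written it cannot be triggered if either arm is stopped first

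*Combined protocol and SAP*

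**What the plan says.** Section 11.0 divides patients into four groups: gastric or non-gastric, at initial presentation or after failure of other treatment.

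- **Goals.** Under *Accrual goals*: "The accrual goals for the patients at initial presentation are 40 for gastric and 35 for non-gastric MALT lymphoma". No goal is given for the two prior-failure groups, where "Accrual of less than 5 patients per year for either gastric or non-gastric MALT lymphoma is expected for presentation upon failure" of other treatment.
- **Untreated arms.** Under *Stopping Rules for patient accrual at initial presentation*: "RFS will be evaluated in each of the two subgroups of previously untreated patients and accrual stopped" if "RFS is < 70% after the first 15, 30, or 45 patients have been followed for a minimum of 2-years".
- **Prior-failure groups.** Under *Stopping Rules for patient accrual upon failure to other treatments*, their data are analysed "When the accrual goals of both gastric and non-gastric MALT lymphoma patients at initial presentation are met". Then: "Decision regarding continued accrual of the patients will be made on the RFS outcome and patient accrual rate at that time". No numerical threshold is attached.
- **Section 2.0 Background** says something different: "The same statistical analysis and stopping rule will apply to the patients who are enrolled in this protocol after failure to initial treatment".

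**The concern.** The trigger requires two events to occur together, and the plan's own stopping rule can prevent either one. An untreated arm stopped for poor RFS at, say, 25 patients will not reach 35 or 40. The condition for reviewing the prior-failure patients then stays unmet. Section 11.0 attaches no consequence for the prior-failure group of the same site, and no enrolment number ends that group. The trigger therefore fails in the situation where a review matters most: radiation alone has just underperformed in newly diagnosed patients. An arm that simply does not fill has the same effect. At stake is the interim decision on whether these patients should go on being enrolled.

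**Working it through.** **Inputs, all from Section 11.0.** Goals are 40 and 35. Accrual is 10–15 a year (gastric), 5–10 a year (non-gastric) and under 5 a year in each prior-failure group. Looks are at 15, 30 and 45 patients with at least 2 years' follow-up, and accrual stops if RFS is below 70%. Of the patients who relapse, 70% do so within 5 years. The stated stopping probabilities are 1%, 17% and 60% at relapse rates of 25%, 50% and 75%.

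**1. Reproducing the plan's stopping probabilities.** Let a fraction R of patients relapse, with exponential relapse times such that 70% of relapses fall within 5 years: λ = −ln(0.30)/5 = 0.241. Then 2-year RFS = 1 − R(1 − e^(−2λ)) = 0.905, 0.809 and 0.713 for R = 25%, 50% and 75%. Simulating 200,000 trials with looks at 15, 30 and 45 gives 1.05%, 16.4% and 59.4% per arm, in line with 1%, 17% and 60%. The plan's sentence could be read as both arms stopping jointly, but that would give 0.01%, 2.7% and 35%, so the figures are per arm. A plain exponential, S(2) = (1 − 0.7R)^0.4, gives 0.4%, 8.2% and 44.7% and does not match. It is kept below as a second case because *Accrual goals* assumes an exponential.

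**2. When a look can come before the goal.** At a constant accrual rate a, with no pause for looks, the n-patient look falls at n/a + 2 years and the goal N is met at N/a. The look comes first only if a < (N − n)/2.

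- 15-patient look: a < (40 − 15)/2 = 12.5 a year (gastric); a < (35 − 15)/2 = 10 a year (non-gastric).
- 30-patient look: a < 5 a year (gastric) and a < 2.5 a year (non-gastric), both below the planned ranges.

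On planned rates, only the 15-patient look can block the trigger. It can do so over the lower half of the gastric range and all of the non-gastric range except its upper end.

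**3. Chance of a stop at the 15-patient look.** RFS below 70% means 10 or fewer of 15 relapse-free, that is, 5 or more relapses. Per arm, p = P(X ≥ 5), with X binomial (15, 1 − S(2)). For at least one of two independent arms, the chance is 1 − (1 − p)².

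| Relapse rate | Matching model: one arm | Matching model: either arm | Plain exponential: one arm | Plain exponential: either arm |
|---|---|---|---|---|
| 25% | 1.1% | 2.1% | 0.4% | 0.7% |
| 50% | 14% | 26% | 7.5% | 14% |
| 75% | 44% | 68% | 34% | 56% |

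The either-arm columns need both arms to accrue below the limits in step 2. If gastric accrual is 12.5 a year or more and non-gastric is below 10, the one-arm columns apply. At 15 and 10 a year, the chance by this route is zero.

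**4. If everything fills.** Goals are met at 40/15 = 2.7 to 40/10 = 4.0 years (gastric) and 35/10 = 3.5 to 35/5 = 7.0 years (non-gastric). The review waits for the slower arm, so it comes at about 3.5 to 7 years. By then, up to 5 × 3.5 = 17.5 to 5 × 7 = 35 patients per prior-failure group could be enrolled (upper bounds, since the stated rate is below 5).

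**5. If Section 2.0 governs.** A 15-patient look within a prior-failure group falls at 15/a + 2 years. At the ceiling of 5 a year that is 5 years; at assumed rates of 3, 2 and 1 a year it is 7, 9.5 and 17 years.

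**The case against.** A reader might infer that prior-failure patients would go on enrolling unexamined, and that the trial could not answer that half of Objective 1.1. The documents do not support this, for three reasons.

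- Section 2.0 applies the same stopping rule to these patients. On that text they have RFS looks of their own that do not depend on the untreated arms.
- Section 11.0 plans outcome analyses in all four groups without condition, so the final analysis is not lost.
- Toxicity oversight (Sections 8.5, 11.0 and 12.1) covers every patient.

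The early-stop route is also narrow. At the plan's expected relapse rate of 25%, it has at most about a 2% chance, and at the top planned accrual rates it has none. The documents give no probability for an arm failing to fill.

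All of this stands as a limit on the point, but it does not remove it. The operative rule in Section 11.0 names only previously untreated patients and then gives prior-failure patients a different rule, so Section 2.0 contradicts Section 11.0 and does not close the gap. Even if Section 2.0 governs, the first look comes no earlier than about 5 years, and stopping an untreated arm still has no stated effect on the matching prior-failure group. Toxicity review addresses harm, whereas this accrual decision rests on RFS and accrual rate. The low chance at 25% is also limited comfort, because a stopping rule is written for the case where that expectation proves wrong.

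**Conclusion.** The trigger is faulty as written: it can fail when an untreated arm is stopped early, and nothing in Section 11.0 replaces it. The loss is confined to the interim RFS-based accrual decision for prior-failure patients. Where both arms accrue slowly enough for the 15-patient look to come first, the chance is about 2%, 26% and 68% at relapse rates of 25%, 50% and 75% (0.7%, 14% and 56% under a plain exponential). These figures assume independent arms, constant accrual without a pause, and RFS judged as the proportion relapse-free at 2 years. Separately, Sections 2.0 and 11.0 disagree on which RFS stopping rule applies to these patients and must be reconciled. The repair is worth making because it is cheap and protects the unfavourable scenario.

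**What to change.** Reword the trigger in Section 11.0 so that the prior-failure data are analysed at the earlier of:

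- (i) both initial-presentation accrual goals being met; or
- (ii) accrual to either initial-presentation arm being stopped under the RFS rule, or closed for any other reason.

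Reconcile Section 2.0 with the two stopping-rule paragraphs of Section 11.0, so that one statement says which RFS rule applies to prior-failure patients. Whether their accrual is held during the review is for the sponsor to decide.

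The cost is one or two sentences and, if (ii) occurs, an earlier tabulation of data already collected. That tabulation would rest on few patients. Within the planned rates, a blocking 15-patient look falls between 15/12.5 + 2 = 3.2 years and 15/5 + 2 = 5 years. Fewer than 5 × 1.2 = 6 to 5 × 3 = 15 patients per prior-failure group would then have 2 years' follow-up, so it should be read as descriptive.

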## **12.0 Reporting Requirements**

- 12.1 Any life-threatening and/or unexpected and serious (Grade 4 or 5) toxicity will be reported immediately to the study chair who in turn must notify the Surveillance Committee.

